Acquisition of images: Studies will be performed with a 3T GE MR system (GE Healthcare, Milwaukee, WI) using a standard quadrature head coil. A high-resolution, T1-weighted 3D anatomical scan will be acquired for each subject (IR-SPGR, TR=9 ms, TE=1.9 ms, TI=500 ms flip angle=10°, matrix= 256×256, FOV=220 mm², 124 1.7 mm thick coronal slices) for coregistration to functional data. Functional images were acquired with a gradient-echo T2 Blood Oxygenation Level Dependent (BOLD) contrast technique, with TR=14000 ms (as a clustered volume acquisition of 2000 ms, plus an additional 12000 ms silent interval), TE=30 ms, FOV=220 mm², 642 matrix, 31 slices, 4 mm thick, no gap, angled parallel to the planum sphenoidale. Additionally, one IR-EPI (TI=505 ms) volume was acquired to improve coregistration between EPIs and the IR-SPGR. Head motion will be minimized with a VacFix headconforming vacuum cushion (Par Scientific A/S, Odense, Denmark). MR-compatible goggles (Resonance Technology, Inc, CA, USA) will be used for visual stimuli.

fMRI Image Analysis Pathway: Images will be preprocessed and analyzed using SPM12 (www.fil.ion.ucl.ac.uk/spm/). Images will be realigned to the first volume, normalized to the Montreal Neurological Institute template, smoothed at 6mm full width at half maximum Gaussian kernel. Data will be preprocessed with slice time correction and modeled with a hemodynamic response convolved function using the general linear model, including temporal and dispersion derivatives. A 128-second high-pass filter will be applied for low-frequency BOLD signal fluctuations, and motion parameters as first-level analysis regressors.

Description of how hypotheses will be tested, including neurocomputational modeling approaches. This study tests the brain response in controls compared to ILL AN women. The paradigm will test reward-learning related brain activation in response to taste stimuli. There will be a primary and a secondary analysis pathway in the paradigm.

The primary analysis pathways will use the methods described in the above fMRI analysis pathway sections. For the taste paradigm this primary analysis will identify brain region activation in response to the conditioned fractal or unconditioned sweet taste application as well as brain response when no taste is received but expected. Main effect results will be obtained for condition and subject group, as well as time activity curve

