data that illustrate brain activation over time in response to the individual stimulus. *The secondary analysis pathway* includes mathematical models that try to bridge brain function and actual behavior. Computational modeling tries to explain a real world problem in a simplified model that then gets translated into a mathematical equation that can be used to correlate with brain imaging results. This serves the purpose of predicting brain response following a stimulus and depending on factors such as learning rate and received reward, different brain regions will be implicated. That is, the subject performs a specific task or Reward Paradigm and learns under what conditions reward occurs (Figure 3.5). The time course of reward experience is known by the experimenter. In the taste experiment, reward delivery or omission is part of the paradigm and recorded by the stimulus-applying computer.

[figure not shown]

Figure 3.5. Practical application of computational modeling of fMRI data.

Use of mathematical models and testing of alternate models. Taste paradigm: For this paradigm we will use the temporal difference model as described in the past in the original description of this paradigm (O'Doherty et al., 2003). On each trial, the predicted value (V) at any time t within a trial is calculated as a linear product of the weights w_i and the presence or absence of a CS

stimulus at time t , coded in the stimulus representation vector $x_i(t)$:

Learning occurs by updating the predicted value of each time point t in the trial by comparing the value at time $t+1$ to that at time t , leading to a prediction error or $\delta(t)$:

where $r(t)$ = reward at time t . The parameter γ is a discount factor, which determines the extent to which rewards that arrive earlier are more important than rewards that arrive later on. Similar to O'Doherty's study (O'Doherty et al., 2003), we will set $\gamma=0.99$. The weights w_i will be then updated on a trial-by-trial basis

$$\Delta w_i = \alpha \sum_t x_i(t) \delta(t)$$

according to the correlation between prediction error and the stimulus representation:

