where α = learning rate. We will assign six time points to each trial and use each subject's individual event history as input. On each trial, the CS (visual fractal) will be taken to be delivered at time point 1, and the UCS reward (sweet taste stimulus) will be delivered at time point 3. We will, as in O'Doherty (O'Doherty et al., 2003), use as learning rate of the model (α) two values for α : a lower learning rate ($\alpha=0.2$) and a higher learning rate ($\alpha=0.7$). In the original study the lower learning rate modeled best brain activation in the ventral striatum and orbitofrontal cortex. The temporal difference error $\delta(t)$ will be created for the CS and the positive and negative UCS for each time-point and an ideal activation curve will be created and convolved with the hemodynamic response curve. That curve will then be modeled to the functional magnetic resonance imaging data in order to generate brain regions that respond according to the model. Time activity curves will then be created in order to compare actual with predicted brain response over time. We cannot predict whether anorexia nervosa women will have simply reduced brain response to the stimuli or if a different learning rate will apply and explain altered learning response. This will be an empirical task during data analysis.

Reversal Learning Paradigm. We adapted a probabilistic reversal paradigm from Cools et al. (Cools et al., 2002). This task has been associated with DA D2 receptor function (Jocham et al., 2009), which is why we selected it for this study design. On each trial, subjects are presented simultaneously with two abstract visual patterns in the left and right visual fields (location randomized). On each trial, the same two patterns are

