presented. One of the patterns is “correct”, and the other pattern is “wrong”. Using trial-and-error feedback, subjects must discover which of the two patterns is correct, using the left or right button on a button response box. On each trial, the stimuli are presented for 2000 msec within which the response has to be made. Feedback, consisting of a green smiley face and “win \$1” for correct responses or a red sad face and “lose \$1” for incorrect responses, will be presented immediately after the response. After feedback, the stimuli will be removed and the faces replaced by a fixation cross for a variable interval (average inter-stimulus interval is 3200 msec). Each block consists of 10 discrimination stages, and therefore, 9 reversal stages. Reversal of the stimulus-reward contingency occurs after between 10 and 15 correct responses (including probabilistic errors). The number of probabilistic errors between each reversal varies from 0 to 4. To prevent subjects from adopting a strategy such as always reversing after two consecutive errors, probabilistic negative feedback is given on two consecutive trials once during each task block. Each block lasts about 8.5 min, total number of blocks is three. **Reversal Learning Task Data Modeling.** The following contrasts will be modeled: (1) final reversal error trials minus correct responses, (2) other preceding reversal error trials minus correct responses, (3) probabilistic error trials minus correct responses, (4) final reversal error trials minus other preceding reversal errors, and (5) final reversal error trials minus probabilistic errors (Cools et al., 2002).

Dopamine Challenge Drugs Amisulpride and Bromocriptine

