All paper data will be stored in locked cabinets in the PI office space at UC San Diego Health Eating Disorders Center for Treatment and Research ([name]). All electronic data will be stored on the VRD server created for [name] lab by the ACTRI (see section 16 PRIVACY AND CONFIDENTIALITY CONSIDERATIONS INCLUDING DATA ACCESS AND MANAGEMENT below for more details).

We will extract for both tasks mean parameter estimates from 18 predefined anatomical regions of interest (ROIs) (<http://marsbar.sourceforge.net/>), automated anatomical labeling Atlas, AAL (Tzourio-Mazoyer et al., 2002) based on previous studies (DeGuzman et al., 2017): dorsal and ventral anterior insula, caudate head, gyrus rectus, medial, middle and inferior OFC, ventral striatum (O'Doherty et al., 2004) and nucleus accumbens (Breiter et al., 1997). Extracted ROI data will be analyzed using SPSS 24 (IBM statistical software) using repeated measures ANCOVA. Extracted regional brain activation parameter estimates will be tested for normality with the Shapiro-Wilk test, rank-transformed when non-normally distributed and analyzed using repeated measures ANCOVA with covariates as in previous studies to account for confounding factors such as comorbidity or medication (DeGuzman et al., 2017). Spearman's rank will be used for correlation analyses and controlled for multiple comparisons using bootstrapping (1000 samples) (Westfall, 2011). We will also conduct exploratory whole-brain analyses to test for areas of interest outside of our predefined ROIs and create PE response maps, with maps thresholded at voxel level $p < 0.05$, FWE corrected (very stringent), 10 voxel minimum cluster contiguity, as well as voxel level $p < 0.001$ and $p < 0.05$ cluster level corrected (exploratory),

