Statistical Power. This is a developmental grant application and we cannot be certain whether the study has sufficient power. However, previous studies using comparable designs and similar sample sizes showed significant within and between group results (Diederer et al., 2017). Studies from our group (Frank et al., 2018a) indicated that subject groups of 20 per group should provide sufficient power based on for instance caudate nucleus PE parameter estimate means of 67.8 (adolescent AN) and 40.2 (adolescent controls), with a mean standard deviation of 28, to reach a power of 0.8, $p<0.05$. Thus, our sample size for the fMRI study should be adequate and be able to replicate our previous results (elevated PE) and provide adequate pilot data for the new analyses in this application. A main goal of this application to investigated data distribution, standard deviation, etc. for future studies.

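### The drug tests on 18 regions of interest in each task carry no multiplicity control, and no prediction-error measure or reversal contrast is designated to test the drug hypotheses

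*Combined protocol and SAP*

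**What the plan says.** All references are to the combined protocol and SAP.

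- **Section 6, Specific Aims.** The PE hypotheses under Aims 1 and 2 name ventral striatum and insula. The reversal hypotheses name striatum. Both give a direction against placebo in AN.
- **Section 9, Data Storage and Data Analysis Plan.** For both tasks the plan extracts "mean parameter estimates from 18 predefined anatomical regions of interest (ROIs"; then, "Extracted ROI data will be analyzed using SPSS 24 (IBM statistical software) using repeated measures ANCOVA". No adjusted alpha, testing order or primary ROI follows. The same paragraph says "Spearman's rank will be used for correlation analyses and controlled for multiple comparisons using bootstrapping (1000 samples", and sets family-wise or cluster-level thresholds for the exploratory whole-brain maps. The available text ends on a comma in that whole-brain sentence.
- **Section 9, Statistical Power.** The only p-value threshold attached to an ROI estimate is 0.05, used to justify 20 per group from "caudate nucleus PE parameter estimate means of 67.8 (adolescent AN) and 40.2 (adolescent controls".
- **Section 9, fMRI Design and hypothesis testing.** "There will be a primary and a secondary analysis pathway in the paradigm". The primary pathway includes the response to an expected but omitted taste. The secondary pathway "includes mathematical models that try to bridge brain function and actual behavior", here a temporal-difference model run at learning rates 0.2 and 0.7. The plan notes that the lower rate fitted ventral striatum and orbitofrontal cortex best in an earlier study. It says it cannot predict whether AN shows a reduced response or "if a different learning rate will apply and explain altered learning response. This will be an empirical task during data analysis".
- **Section 9, Reversal Learning Task Data Modeling.** "The following contrasts will be modeled: (1) final reversal error trials minus correct responses", followed by four more. None is ranked.

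**The concern.** The plan recognises multiplicity in its correlations and its exploratory maps, but leaves the ROI tests, which bear directly on the drug hypotheses, without a rule. An analyst who follows the text at 0.05 per test can look for a drug effect in any of 18 regions, on either of two kinds of PE measure, at either learning rate and in any of five reversal contrasts. The plan does not say which result would count. It also does not say whether the PE hypothesis needs ventral striatum, insula or both.

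The stake is interpretation. The lay summary expects the results to support D2 receptor involvement directly, and a chance finding in one region could be reported that way.

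**Working it through.** **1. The plan's own figure.** The difference is 67.8 - 40.2 = 27.6, and 27.6 / 28 = 0.986 SD. A two-sided two-sample t-test at 0.05 with 80% power needs 17.2, so 18 per group; 20 per group gives 86%. The stated 20 is reproduced and slightly conservative. It describes one AN-control test in one region (caudate), so it sets no error rate for drug-placebo tests.

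**2. Inputs for the error rate.**
- From the plan: 18 ROIs; 20 per group; two drugs compared with the same placebo scan.
- Assumed, because the plan does not say: one model per ROI; two-sided 0.05 per test; no drug effect; a common inter-ROI correlation of 0, 0.5 or 0.8.
- Inferred: nine regions are listed, so 18 probably means 9 x 2 sides.

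**3. Formula.** For each ROI and drug, t = mean(drug - placebo) / (SD of the differences / √20), rejected if |t| > 2.093 (19 df). The family-wise rate is the chance that at least one ROI rejects. With independent ROIs it is 1 - 0.95^k:
- k = 18: 1 - 0.95^18 = 0.603
- k = 3: 1 - 0.95^3 = 0.143
- k = 6: 1 - 0.95^6 = 0.265

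For correlated ROIs, and for two drugs sharing a placebo scan, the rate was simulated (20,000 or more replicates).

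| ROIs tested | One drug, correlation 0 / 0.5 / 0.8 | Either drug |
|---|---|---|
| All 18 | 60 / 42 / 23% | 82 / 63 / 38% |
| Named PE regions, sides separate (6) | 26 / 21 / 14% | 44 / 36 / 25% |
| Named PE regions, sides averaged (3) | 14 / 13 / 10% | 25 / 22 / 18% |

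The named PE regions are taken as ventral striatum and the dorsal and ventral anterior insula. Repeated runs differ by about one point. If left-right pairs correlate 0.8 and different regions 0.3 to 0.5, the 18-ROI rate is about 38-47% for one drug and 59-69% for either. With 22 AN subjects (half of the 44 planned completers, an assumed split) no figure in the table moves by more than about two points.

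**4. Predicted direction only.** Counting only results in the hypothesised direction, the one-drug rate is 7 / 6 / 5% for three ROIs and about 14 / 11 / 7% for six.

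**5. If both regions must respond.** Suppose the drug truly affects ventral striatum but not insula. The insula part alone then decides, and it is itself a choice among ROIs. Its two-sided error is about 8-10% with two insula ROIs and 12-19% with four.

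**6. Learning rates and contrasts.** Their added effect is not quantified, because the documents give no correlations between them.

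**7. Power cost of Holm, as illustration.** The documents give no within-subject SD. Take the standardised paired effect that gives 80% power at n = 20, dz = 0.66 (noncentrality 0.66 x √20 = 2.95):
- Three ROIs x two drugs = 6 tests; first step 0.05/6 = 0.0083; power 52%.
- Six ROIs x two drugs = 12 tests; first step 0.05/12 = 0.0042; power 41%.

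At n = 22 the same effect gives 84% unadjusted, then 58% and 47%.

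**The case against.** Several points on the other side have force.

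- **It is a pilot.** Aims 1 and 2 are framed as feasibility and acceptability, Aim 3 as pilot data, and the power section calls the study developmental. Strict family-wise control is therefore not obligatory. This stands, and it is why the fix leaves adjustment to the sponsor. It does not remove the need to say which tests bear on the directional hypotheses.
- **Regions and direction are already named.** This also stands. A reader might take 60% or 82% as the error rate of the drug hypotheses. The documents do not support that: those figures need independent ROIs, one model per ROI, and any region in either direction counting. A single model with region as a factor is equally possible. Pooling the two drugs also merges two separate aims. However, the analysis plan never carries the restriction to named regions forward.
- **PE is not confined to the secondary pathway.** A reader might infer that it exists only in the temporal-difference model. The fMRI Design text lists received versus omitted reward as a variable of interest, and the primary pathway includes the response to omission, so a measure without any learning rate is available. That makes two candidate measures, with neither designated. The remark that the lower rate fitted best reports an earlier result and does not choose a rate.
- **Text may be missing.** The break falls in the whole-brain sentence, and the ANCOVA covariates are referred to an earlier study. The absence of a rule is therefore stated for the text as available.

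**Conclusion.** The concern holds in this form: as available, the plan tests 18 ROIs in each of two tasks without error control, does not limit those tests to the hypothesised regions, and designates neither a PE measure nor a reversal contrast. The inflation comes mainly from the unrestricted ROI set. It is smaller in the named regions, and smaller again if only the predicted direction counts. It would be tempting to add that it disappears once both regions are required, but it does not, because insula covers more than one ROI. All sizes rest on assumed correlations, one model per ROI, 0.05 per test and about 20 AN subjects. The planned pilot description of distributions and standard deviations is not affected. This should be settled before analysis, but it does not invalidate the design.

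**What to change.** Before analysis:

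1. Limit the tests of the drug hypotheses in AN to the regions named in the Specific Aims. State whether left and right are averaged, whether nucleus accumbens counts as ventral striatum, and whether one region or both must respond. If both, designate one insula ROI or adjust over the insula ROIs.
2. Designate one PE measure (the primary-pathway contrast, or the model at one learning rate) and one reversal contrast in one striatal ROI.
3. Label all other ROIs, rates, contrasts and group-by-drug comparisons exploratory. Report them with 95% confidence intervals and max-T adjusted p-values across the 18 ROIs, extending the 1000-sample bootstrap already planned for the correlations. In a simulation for one drug at n = 20 this gave a family-wise error of about 3%, so it is somewhat conservative.
4. For the designated tests, either adjust within task over the tests actually counted (for example Holm over six, or over twelve if sides are separate), or label them exploratory too and report confidence intervals. Given the pilot status, this choice is the sponsor's.

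The cost is plan wording and a little computing, with no change to study conduct. If Holm is chosen there is also the power loss illustrated above; the exploratory label avoids it.

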6. SPECIFIC AIMS

Aim 1. To establish in AN feasibility and acceptability of a study design to understand the contributions of the selective DA D2 receptor agonist bromocriptine on PE and reversal learning.

Hypothesis 1.a. The DA D2 receptor agonist bromocriptine (1.25mg) will enhance fMRI PE response during a taste-reward PE paradigm in AN in ventral striatum and insula compared to placebo.

Hypothesis 1.b. The DA D2 receptor agonist bromocriptine (1.25mg) will enhance reversal learning and striatum brain response in AN during a monetary reversal learning task compared to placebo during fMRI.

Aim 2. To establish in AN feasibility and acceptability of a study design to understand the contributions of the selective DA D2/D3 receptor antagonist amisulpride on PE and reversal learning.

Hypothesis 1.a. The DA D2 receptor antagonist amisulpride (400mg) will reduce fMRI PE response in the insula and ventral striatum compared to placebo.

Hypothesis 1.b. The DA D2 receptor antagonist amisulpride (400mg) will reduce reversal learning and striatum brain response in AN during a monetary reversal learning task compared to placebo during fMRI.

Aim 3. To gather pilot data how fMRI brain response to the DA D2 receptor agonist bromocriptine or antagonist amisulpride differs between individuals with AN and healthy control women.

Hypothesis 3. We expect we will find an indication that bromocriptine will enhance PE (ventral striatum and insula) and reversal learning (frontal cortex) in AN more compared to the control group, while amisulpride causes the opposite.

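### Rank-transforming non-normal ROI estimates before the repeated-measures ANCOVA can distort the drug and group-by-drug tests, whether ranks are pooled or taken session by session

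*Combined protocol and SAP*

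**What the plan says.** Section 9, Data Storage and Data Analysis Plan, covers 18 predefined ROIs in both tasks. "Extracted regional brain activation parameter estimates will be tested for normality with the Shapiro-Wilk test"; those that fail are "rank-transformed when non-normally distributed" and then analysed by repeated-measures ANCOVA, the covariates being there for confounders such as comorbidity or medication. The plan does not state which values share a ranking, the level of the normality test, or whether that test uses raw values or residuals. It mentions neither aligned ranks nor difference scores.

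Aims 1 and 2 (section 6) compare each drug with placebo within AN. Hypothesis 3 expects bromocriptine to enhance the response "in AN more compared to the control group, while amisulpride causes the opposite". The Statistical Power paragraph of section 9 expects elevated prediction error in AN, citing "caudate nucleus PE parameter estimate means of 67.8 (adolescent AN) and 40.2 (adolescent controls), with a mean standard deviation of 28". The lay summary expects the two drugs to act in opposite directions.

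**The concern.** An interaction is tied to its scale. If AN starts higher and both groups respond to a drug by the same amount, the raw group-by-drug interaction is zero. It need not be zero on ranks, because a rank counts how many other values are overtaken, and few values lie near the ends. The pattern the plan hypothesises, with an elevated patient group and drugs that act in opposite directions, is one in which ranking can bend the interaction.

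At stake are Aim 3, which is the group-by-drug contrast, and Aims 1 and 2, which are drug-versus-placebo contrasts in AN. The scale would also switch ROI by ROI according to a preliminary test, so effects would not be comparable across regions. Ranks also discard the units that a pilot meant to learn distributions and standard deviations has to report.

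**Working it through.** **1. The plan's own figure.** Inputs: "caudate nucleus PE parameter estimate means of 67.8 (adolescent AN) and 40.2 (adolescent controls", "with a mean standard deviation of 28".
- Standardised difference: (67.8 − 40.2)/28 = 27.6/28 = 0.986.
- n per group for power 0.8, two-sided 0.05: 2(1.960 + 0.842)²/0.986² = 16.2, so 17; the t-based formula gives 18.
- At 20 per group: 0.986 × √(20/2) = 3.12; 3.12 − 1.96 = 1.16; power 0.876 (0.859 by t).

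The statement that "subject groups of 20 per group should provide sufficient power" is therefore reproduced. It concerns AN against controls without drug, so it neither covers the interaction nor is affected by this point.

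**2. Simulation inputs.**
- From the documents: three sessions per person, 44 completers (section 10), AN shift 0.986 SD.
- Assumed: 22 per group, within-person correlation 0.5, no covariates, drug shifts of the sizes shown, and normal, t with 3 df, or lognormal (sigma 0.5, 0.8, 1.0) errors.
- Contrast: (AN bromocriptine − AN placebo) − (control bromocriptine − control placebo).

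**3. All 44 × 3 = 132 values ranked together.**

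*Type I error.* Bromocriptine raises and amisulpride lowers both groups equally by 0.5-0.8 SD, so the true interaction is zero. With the Shapiro-Wilk rule applied and non-normal errors, type I error is 6-30%, against 4-5% on the raw scale. The low end is mild skew at 0.5 SD; the high end is lognormal sigma 1.0 at 0.8 SD. If either the group shift or the drug effect is zero, it is about 5%.

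*Power.* Bromocriptine adds 0.8 SD more in AN than in controls. Amisulpride lowers both groups by the size of the controls' bromocriptine response. Errors are non-normal and ranking is applied.

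| Control response | Raw scale | Pooled ranks |
|---|---|---|
| 0.5 SD | 0.73-0.77 | 0.12-0.36 |
| 0.25 SD | 0.73-0.77 | 0.51-0.63 |
| none | 0.73-0.77 | 0.75-0.91 |

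*Other contrasts.* A wider grid used effects of 0.5 to 1.0 SD and correlation 0.5 or 0.8. With non-normal errors and the Shapiro-Wilk rule applied, type I error reached 0.39 for bromocriptine-placebo, 0.30 for amisulpride-placebo and 0.33 for the omnibus test, but only about 0.1 for bromocriptine-amisulpride. With the true interaction scaled to give raw power of 0.80 for the contrast concerned, pooled ranks gave:
- bromocriptine-placebo: 0.09-0.35;
- bromocriptine-amisulpride: 0.44-0.73, with the omnibus test falling from about 0.72 to 0.51-0.67;
- amisulpride-placebo: a rise to 0.86-0.96, because there the distortion runs in the hypothesised direction.

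**4. Each session ranked separately.** This part is mostly exact arithmetic. The ranks 1 to 44 sum to 44 × 45/2 = 990, so every session has mean rank 990/44 = 22.5, whatever the drug does. With 22 per group and group mean ranks A (AN) and C (controls), 22A + 22C = 990, so A + C = 45 in every session. Hence the change in A from placebo to drug is always minus the change in C.
- If both groups shift equally, the ordering within a session is unaffected and the expected AN change is zero. A true shared effect of 0.5-0.8 SD was detected within AN in 0.3-3.5% of runs (raw scale 62-94%).
- If only controls respond, AN is forced to move the other way. A false AN effect appeared in 32-70% of runs.
- The interaction equals twice the AN change. Its type I error stays at 0.03-0.07, but for the 0.8 SD difference its power is about 0.14-0.34 with non-normal errors.

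**5. How often ranking is triggered.** At least one session fails Shapiro-Wilk in about 10-20% of normal data sets and about 65-100% of the non-normal ones. With normal errors and a 0.5 SD control response, power under the rule is 0.65-0.70, against about 0.73 raw (0.42 if ranking were unconditional). Under skew the rule gives little protection; for t errors it raises pooled-rank power from 0.34 to as much as 0.50.

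**The case against.** The strongest reply is that the harm depends on quantities the documents do not give: drug effect in each group, within-person correlation and error shape. Much of this stands.

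- A reader might infer that the rule removes most of the power for Aim 3 in the situation the plan expects. The documents do not support that. They say bromocriptine should act more in AN, not that controls respond. With no control response, pooled ranking does as well as the raw scale or better. The large loss is also confined to bromocriptine against placebo.
- A reader might add the false interaction and the erased drug effect together. They cannot both occur, since one needs pooled ranks and the other session-wise ranks. Under pooled ranks, within-AN power for a 0.8 SD drug effect is 0.93-1.0, so Aims 1 and 2 are then not harmed in this way.
- A reader might suppose that the errors favour the sponsor's hypothesis. In skewed data almost all the false bromocriptine-placebo interactions run against Hypothesis 3; those for amisulpride-placebo run with it.
- The 0.986 SD shift comes from adolescent caudate data, while this trial enrols ages 18 to 29 and names ventral striatum and insula for prediction error. Elevation in AN is stated for prediction error, not for the reversal-learning response.

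What does not stand is that this is only a missing detail. Naming the ranking pool would choose between two problems rather than remove them.

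**Conclusion.** The point holds in conditional form and should be fixed before analysis. With pooled ranks, non-normal errors, an elevated AN group and drug response in both groups, the bromocriptine-versus-placebo interaction test can have type I error of about 6-30% at equal effects of 0.5-0.8 SD. Its power can fall by more than half once controls respond by 0.5 SD. With session-wise ranks the interaction test keeps its level, but an effect shared by both groups cannot be seen within AN, and interaction power is low. When data are normal the harm is small, because ranking is seldom triggered.

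The equal mean rank under session-wise ranking is arithmetic and certain. Every other figure rests on the stated assumptions and should be read as a range. The plan's 20 per group is untouched.

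**What to change.** Replace the ranking rule along these lines: raw ROI estimates will not be rank-transformed. For each person and ROI, drug-minus-placebo differences will be analysed in parameter-estimate units with the planned covariates, testing the mean difference within AN (Aims 1 and 2) and the group difference in differences (Aim 3). If residuals are non-normal, permutation p-values from the same model will be used.

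Add, as unadjusted sensitivity analyses, a Wilcoxon signed-rank test within AN and a rank-sum test on the differences between groups. In the non-normal settings the rank-sum test on differences kept type I error at 0.035-0.065 and had power of about 0.80-0.97 for the 0.8 SD difference. Report all effects in raw units.

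The cost is a few sentences in the plan and a little more analysis work, with no change to data or sample size. The simple rank tests cannot carry the covariates that the plan requires, so they should support the adjusted raw-scale model and not replace it.
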